If a liver biopsy is performed according to the local regulations or standard of care at any time during A4250-008, the biopsy results should be recorded in the electronic case report form (eCRF). If the patient had liver biopsy results collected in study A4250-005 or prior to Week 24 in study A4250-008, the patient will be asked to consent to a follow-up liver biopsy, if allowed per local regulations, at Visit 11, unless 2 prior liver biopsy results have been collected with at least 1 year between biopsies. Liver biopsies will not be performed in Spain.

For those not participating in the optional extension period, Visit 12 will take place 28 days after Visit 11. All patients prematurely withdrawn will have this visit 28 days after the last dose of study drug for AE and other follow-up.

If a patient discontinues prior to Week 72, additional telephone contacts will be made every 3 months after the Follow-up Visit (Visit 12) up to Week 72 to gather whether or not the patient

has had biliary diversion or liver transplantation, and if TEAEs ongoing at the time of discontinuation have resolved. The telephone calls will take place up until 72 weeks even if the patient has biliary diversion or liver transplant.

Details of study assessments are provided in the schedule of assessments ([Table 1](#) and [Table 2](#)).

Figure 1 Study Design

QD: once daily; T: telephone contact; V: study visit; VS: Visit Screening

Note: Visit 1 coincides with Visit 9 of Study A4250-005. Patients who are not tolerating the 120 µg/kg/day dose may be down-titrated to the 40 µg/kg/day dose following a minimum of 1 week of treatment. The patient can return to the higher dose as soon as deemed appropriate.

This figure is only applicable to Cohort 2 up to Protocol Amendment 5. [Figure 2](#) presents the study design for Cohort 2 as of Protocol Amendment 6.

Figure 2 Study Design for Cohort 2 as of Protocol Amendment 6

QD: once daily; T: telephone contact; V: study visit; VS: Visit Screening

Note: As of Protocol Amendment 6, patients entering Cohort 2 will start treatment at 40 µg/kg/day with the possibility to dose escalate to 120 µg/kg/day after 12 weeks if there is no improvement in pruritus based on investigator judgment. The patient can return to the lower dose if the 120 µg/kg/day dose is not tolerated following a minimum of 1 week of treatment.

End of Study

The end of the study is defined as follows:

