		Screening/ Initial Visit	4 weeks	12 weeks	22 weeks	24 weeks	36 weeks	46 weeks	48 weeks	60 weeks	70 weeks	72 weeks		
Study Activity		76 weeks												
Study Days (±window)	-56- (-35) ±2	-28- (-7) ±2	1	28 (±5)	84 (±7)	154 (±7)	168 (±7)	252 (±7)	322 (±7)	336 (±7)	420 (±7)	490 (±7)	504 (±7)	532 (±7)
Clinic Visits	Visit S-1	Visit S-2	Visit 1a	Visit 2	Visit 3	Visit 4	Visit 5	Visit 6	Visit 7	Visit 8	Visit 9	Visit 10	11/EOT /Start of Optmnl Extension Period ¹¹	Visit 12 ^c
Fibroscan (where available)			X				X			X			X	
QoL questionnaire (PedsQL)			X				X			X			X	
Patient/Caregiver/Clinician Patient Global Impression of Change			X ¹¹	X	X		X			X			X	
Patient/Caregiver/Clinician Patient Global Impression of Symptoms				X	X	X	X	X	X	X	X	X	X	
Pregnancy test ¹¹	x ¹¹	X	x ¹¹	X	X	X	X	X	X	X	X	X	X	X
Telephone contact			Patients will be contacted via telephone for adverse event monitoring at Weeks 8, 18, 30, 42, 54, and 66											
Liver biopsy ¹¹													X	
Study drug dispensed ¹¹			X	X	X		X	X		X	X		X ¹¹	

Study Activity	Screening Period (Cohort 2 only)		Treatment Period										Follow-up Period ^h	
			Screening/ Inclusion Visit	4 weeks	12 weeks	22 weeks	24 weeks	36 weeks	46 weeks	48 weeks	60 weeks	70 weeks		
Study Days (\pm window)	-56- (-35) ± 2	-28- (-7) ± 2	1	28 (± 5)	84 (± 7)	154 (± 7)	168 (± 7)	252 (± 7)	322 (± 7)	336 (± 7)	420 (± 7)	490 (± 7)	504 (± 7)	532 (± 7)
Clinic Visits	Visit S-1	Visit S-2	Visit 1a	Visit 2	Visit 3	Visit 4	Visit 5	Visit 6	Visit 7	Visit 8	Visit 9	Visit 10	Visit 11/EOT /Start of Optional Extension Period ⁱ	Visit 12 ^c
Adverse events ^o p	Continuous collection													
Study drug compliance evaluated				X	xq		X	xq		X	X		xq	

eCRF: electronic case report form; eDiary: electronic diary; EOT: end of treatment; p-C4: plasma 7a Hydroxy 4-cholesten-3-one; PedsQL: pediatric quality of life; QoL: quality of life.

a For patients in Cohort I, Visit 1 coincides with Visit 9 in Study A4250-005. Assessments that have been performed at Visit 9 during Study A4250-005 will not be repeated.

b Assessments must also be performed at the time a patient is prematurely withdrawn from the study. If a patient discontinues prior to week 72, additional phone contact will be made every 3 months up to a total study participation of 72 weeks to assess if the patient has had biliary diversion or liver transplantation.

c Assessments must be performed 28 days following the final dose of study drug.

d Only for Cohort 1.

e Includes current medications.

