7.2.3 Withdrawal of Patients

Patients/caregivers will be informed that they have the right to withdraw from the study at any time, without prejudice to their medical care, and that they are not obliged to state their reasons.

Any withdrawal, and reasons for withdrawal, must be fully documented in the eCRF and source documents and the patient followed by the investigator/investigative staff. Withdrawn patients will not be replaced.

Patients will be withdrawn in the following circumstances:

- A patient's/caregiver's desire for withdrawal for any reason
- Lost to follow-up (every effort must be made to contact the patient/caregiver; a certified letter must be sent)
- An AE which, in the opinion of the investigator, necessitates withdrawal
- Death
- A patient's/caregiver's substantial non-compliance (eDiary and study drug compliance) or protocol violation
- An investigator's opinion that continuing the patient in the study is not appropriate. The investigator may withdraw a patient at any time, if it is considered to be in the patient's best interest
- Liver transplantation

The reason and the date the patient is withdrawn from the study will be documented in the eCRF and source documents. If a patient is withdrawn from further treatment with the study drug, the investigator/investigative staff will attempt to complete all Visit 11 procedures at the time the patient is prematurely withdrawn from the study. The investigator/investigative staff will also attempt to complete all Visit 12 procedures 28 days following premature withdrawal (i.e., 28 days following the final dose of the study drug).

If a patient discontinues prior to Week 72, additional telephone contacts will be made every 3 months after the Follow-up Visit (Visit 12) up to Week 72 to gather whether or not the patient has had biliary diversion or liver transplantation, and of ongoing TEAEs at the time of discontinuation have resolved. The telephone calls will take place up until 72 weeks even if the patient has biliary diversion or liver transplant.

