9.1.2 Secondary Efficacy Endpoints

EU and rest of world: Proportion of positive pruritus assessments at the patient level over the 72-week treatment period using the Albireo ObsRO instrument.

US: Change from baseline in serum bile acids after 72 weeks of treatment.

All Regions:

- Change from baseline in serum bile acids at Weeks 4, 12, 22, 24, 36, 46, 48, 60, 70, 72, and 76
- Proportion of individual assessments meeting the definition of a positive pruritus assessment at the patient level using the Albireo ObsRO instrument from Weeks 0-4, Weeks 0-12, Weeks 0-22, Weeks 0-24, Weeks 0-36, Weeks 0-46, Weeks 0-48, Weeks 0-60, and Weeks 0-70, respectively, or the proportion of positive pruritus assessments at each 4-week interval between Visit 1/Screening and Visit 5/Week 24, then by each visit between Visit 5/Week 24 to Visit 12/Week 76
- Proportion of individual AM assessments meeting the definition of a positive pruritus assessment at the patient level using the Albireo ObsRO instrument from Weeks 0-4, Weeks 0-12, Weeks 0-22, Weeks 0-24, Weeks 0-36, Weeks 0-46, Weeks 0-48, Weeks 0-60, Weeks 0-70, and Weeks 0-72, respectively, or the proportion of positive pruritus assessments at each 4-week interval between Visit 1/Screening and Visit 5/Week 24, then by each visit between Visit 5/Week 24 to Visit 12/Week 76
- Proportion of individual PM assessments meeting the definition of a positive pruritus assessment at the patient level using the Albireo ObsRO instrument from Weeks 0-4, Weeks 0-12, Weeks 0-22, Weeks 0-24, Weeks 0-36, Weeks 0-46, Weeks 0-48, Weeks 0-60, Weeks 0-70, and Weeks 0-72, respectively, or the proportion of positive pruritus assessments at each 4-week interval between Visit 1/Screening and Visit 5/Week 24, then by each visit between Visit 5/Week 24 to Visit 12/Week 76
- All-cause mortality, number of patients undergoing biliary diversion surgery or liver transplantation. These parameters will be evaluated separately and together at weeks 24, 48, and 72

- Change in growth from baseline to Weeks 24, 48, and 72 after initiation of A4250 treatment, defined as the linear growth deficit (height/length for age, weight for age, mid-arm circumference, and body mass index [BMI]) compared to the standard growth curve (Z-score, standard deviation [SD] from P50)
- Change in AST to platelet ratio index (APRI) score and Fib-4 score from baseline to Week 72

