10.1.2 Recording of Adverse Events

It is the investigator's responsibility to assess whether each untoward event is a clinically significant worsening from baseline, thereby considered an AE. For all AEs, the severity, seriousness, and causality to study drug for each AE as outlined in [Section 10.1.1](#) will be assessed and recorded in the eCRF.

All serious and non-serious AEs are collected once the caregiver/patient has signed the ICF and until the post-treatment follow-up (Visit 12), 28 days after the last dose of study drug. Collection of all serious and non-serious AEs will continue for the optional extension period.

Any AEs or SAEs that are unresolved at the patient's last AE assessment in the study are followed up by the investigator until resolution or stabilization up to the database lock and

recorded in the eCRF. Albireo retains the right to request additional information for any patient with ongoing AE(s) or SAE(s) at the end of the study.

TEAEs that are ongoing at time of discontinuation will be followed up until week 72 by telephone calls every 3 months. No new AEs will be recorded after the patient has permanently discontinued study drug.

TEAEs are defined as any AE that occurs after dosing (Day 1), including new AEs or the worsening of an event after the first dose.

If there is a clinically significant deterioration of a laboratory value/vital sign or other routine study assessment that is associated with a diagnosis, the clinical diagnosis will be reported as an AE and the associated signs and symptoms will be considered additional information unless the sign or symptom is more severe than expected given the diagnosis. For example, if an investigator diagnoses a study patient with hepatitis during the study period, hepatitis would be considered the AE and the concomitant signs and symptoms of abdominal pain, vomiting, and elevated ALT and AST would not be reported separately unless, in the opinion of the investigator, one of these signs or symptoms is more severe than expected and therefore a separate AE assessment is indicated.

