11.2.2.6 Evaluation of Secondary and Exploratory Efficacy Variables

All secondary and exploratory variables listed under [Sections 9.1.2](#) and [9.1.3](#) will be analyzed descriptively for categorical and continuous data, as applicable. For continuous data, the change from baseline will be analyzed in addition to the actual visit values. For categorical data, shift tables or frequency and percentages of patients will be presented as appropriate.

Change in growth (Z-score, SD from P50 standard growth curve) will be analyzed by using one-sample T-test or Wilcoxon signed-rank test as appropriate. Change in growth (height/length for age, weight for age, BMI, and mid-arm circumference) will also be displayed using graphical presentations.

A 95% CI will be calculated for the proportion of patients experiencing surgical bile diversion or liver transplantation or death as well as for the proportion of patients experiencing surgical bile diversion or death or liver transplantation. The upper boundary will be compared to the

expected proportion of events, using the event probability estimated from the untreated reference population in an ongoing observational cohort study.

Time to first event, i.e., time to surgical bile diversion or liver transplantation or death, will be explored by descriptive statistics and Kaplan-Meier curves, which also will be used to make a comparison to the NAPPED population. The propensity score matched cohort analysis using inverse probability of treatment weights will be used to match the study patient population to the reference population based on age group and PFIC type.

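### Follow-up calls after early discontinuation are not tied to Week 72, so diversion and transplant status can be unknown for up to just under 13 weeks before the endpoint date

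*Protocol*

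**What the plan says.** Section 7.2.3 (Withdrawal of Patients) states that, for a patient who discontinues before Week 72, "additional telephone contacts will be made every 3 months after the Follow-up Visit (Visit 12) up to Week 72". The calls ask about biliary diversion, liver transplantation and whether ongoing TEAEs have resolved. The same section adds: "The telephone calls will take place up until 72 weeks even if the patient has biliary diversion or liver transplant". Section 7.1.1 repeats the rule and dates Visit 12: "All patients prematurely withdrawn will have this visit 28 days after the last dose of study drug for AE and other follow-up". Table 1, footnote b, in Section 7.1.2 gives the interval but no Visit 12 anchor: "additional phone contact will be made every 3 months up to a total study participation of 72 weeks".

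The endpoint these calls serve is in Section 9.1.2: all-cause mortality, biliary diversion and liver transplantation. On timing it says "These parameters will be evaluated separately and together at weeks 24, 48, and 72". Section 11.2.2.6 plans a 95% CI for the event proportion and continues "The upper boundary will be compared to the" proportion expected from the untreated reference population. It also says: "Time to first event, i.e., time to surgical bile diversion or liver transplantation or death, will be explored by descriptive statistics and Kaplan-Meier curves", again with a comparison to the reference cohort.

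No section schedules a status contact at Week 72 for a patient who stopped early.

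**The concern.** The endpoint needs each patient's status at Week 72. The calls run at a fixed interval from a date that differs between patients, and Week 72 only marks where the series ends. Unless the interval happens to land on Week 72, the last weeks are unobserved.

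Gaps between calls do little harm, because the next call covers them, including for the Week 24 and Week 48 evaluations. The loss is the terminal gap from last contact to Week 72. A diversion or transplant in that gap may never be learned of, and an unascertained event can only lower the observed count. In a single-arm comparison with an external cohort, that direction favours A4250. An analysis plan can choose how to treat patients with unknown status, but it cannot recover events that nobody asked about.

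**Working it through.** **The plan's own figure.** Section 11.1 gives power of about 89% to 96% for an upper CI bound below 30% when the true event rate is 10%, with n=48 to 60. An exact binomial calculation with a Clopper-Pearson upper bound reproduces it:
- n=48: at most 7 events allowed, power 89.8%.
- n=60: at most 10 events allowed, power 96.6%.

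The power statement is not in question.

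**Call schedule.** Inputs: last dose at Week D; Visit 12 at D+4 (Sections 7.1.1 and 7.2.3); calls every 3 months, taken as 13 weeks, from Visit 12 and not beyond Week 72.
- First call: D + 4 + 13 = D + 17. This is by Week 72 only if D ≤ 55.
- Visit 12 itself reaches Week 72 when D ≥ 68.
- So for 55 < D < 68 there is no call after Visit 12, and the gap is 72 − (D + 4) = 68 − D weeks.
- For all D up to 68, the terminal gap is (68 − D) mod 13.

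| Last dose (week) | Visit 12 | Calls (week) | Gap to Week 72 (weeks) |
|---|---|---|---|
| 4 | 8 | 21, 34, 47, 60 | 12 |
| 16 | 20 | 33, 46, 59, 72 | 0 |
| 30 | 34 | 47, 60 | 12 |
| 50 | 54 | 67 | 5 |
| 55 | 59 | 72 | 0 |
| 56 | 60 | none | 12 |
| 60 | 64 | none | 8 |
| 64 | 68 | none | 4 |
| 68 | 72 | none needed | 0 |

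**Average gap.** Assume D is uniform over Weeks 0-68, which is five full 13-week cycles plus 3 weeks.
- Mean gap = (5 × 13 × 6.5 + 3 × 1.5) / 68 = 427 / 68 = 6.3 weeks.
- Share with no call = 13 / 68 = 19%.

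**Sensitivity to the reading.**
- 3 months as 12 weeks: no call for stops strictly between Weeks 56 and 68 (12/68 = 18%); mean gap (5 × 12 × 6 + 8 × 4) / 68 = 392 / 68 = 5.8 weeks; maximum just under 12.
- Calls counted from discontinuation, as footnote b allows: first call at D + 13, so no call for stops between about Weeks 59 and 68 (9/68 = 13%); mean gap (4 × 84.5 + 24.5 + 40.5) / 68 = 403 / 68 = 5.9 weeks; maximum still just under 13.

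**Possible missed events (illustration).** The protocol gives neither a discontinuation rate nor an event rate after stopping. Assume 20 of about 120 patients stop early and that the 30% untreated example applies over 72 weeks.
- Hazard = −ln(0.7) / (72/52) = 0.357 / 1.385 = 0.26 per year.
- Missed events = 20 × (6.28/52) × 0.26 = about 0.6.
- Same stopping fraction (1 in 6) on the example's n=48 to 60: 8 to 10 stoppers, about 0.25 to 0.31 missed events, against 4.8 to 6 events at the 10% rate.

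**Sensitivity of the comparison.** Exact upper bounds: n=48, 7 events 27.8%, 8 events 30.2%; n=60, 10 events 28.5%, 11 events 30.4%. At that margin, one event decides which side of 30% the bound falls.

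**The case against.** Several points on the other side have force.

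- **The intended end is Week 72.** All three descriptions carry follow-up to that week, and a reader could take the end limit as including a closing call. That is a fair reading of intent, but a site applying a 3-monthly interval has no instruction to call then.
- **Other contacts exist.** Section 7.2.3 has withdrawn patients followed by site staff. Section 11.2.2.2 promises efficacy collection after discontinuation as far as possible. Section 10.2.2.8 requires weekly monitoring after a safety discontinuation until values normalise or stabilise. Section 10.1.2 follows unresolved AEs up to database lock. These will catch some events, so the calls are not the only source. None is dated to Week 72 or covers every early stopper. New AE reports do not fill the gap: "No new AEs will be recorded after the patient has permanently discontinued study drug". Even the collection to Visit 12 in the same section ends where the gap begins.
- **Some early stoppers already have their event.** Death and liver transplantation are themselves withdrawal reasons, recorded with dates. The illustration does not remove these patients, so it is probably too high.

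A reader might infer more than the document supports:

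- **That unreached patients are counted event-free.** No section says so. Section 11.2.2.2 says imputation will in general not be made and leaves missing-data handling to the SAP, and Kaplan-Meier ordinarily censors at last contact.
- **That early stoppers are the patients most likely to need surgery, with rates of 0.5 to 1.0 per year.** The document gives no such rate. Those figures would yield 1.2 to 2.4 missed events, but they are about 2 to 4 times the untreated hazard implied by the protocol's own example.
- **That stopping between Weeks 55 and 68 is a second, worse defect.** These patients still have Visit 12 scheduled, and their gap lies in the same range as everyone else's.

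**Conclusion.** The point holds as a gap in data collection. On a literal reading, status is unknown for 0 to just under 13 weeks before Week 72 for most stop dates, about 6 weeks on average under uniform stopping. Patients stopping strictly between Weeks 55 and 68 get no call after Visit 12; the window is about Weeks 59 to 68 if calls run from discontinuation. The interval and anchor conventions change these figures only slightly.

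The effect on the count can only be downward, but its size is not determined by the document. About 0.6 events is an illustration resting on two assumptions, and it does not allow for the other contacts or for patients withdrawn with an event. How far a missed event would bias the proportion or the Kaplan-Meier curve also depends on SAP rules not shown. This is a secondary endpoint in an open-label study without formal hypothesis testing, so the weight is moderate. The change is worthwhile because it is cheap and the information cannot be recovered at analysis.

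**What to change.** In Sections 7.1.1 and 7.2.3 and in Table 1, footnote b:
- Keep the 3-monthly calls, with one common anchor stated in all three places.
- Add one status contact at Week 72 (Day 504, with the ±7-day window already used for Visit 11) for every patient who stopped early and has not refused contact.
- Record at that contact the date of any biliary diversion or liver transplantation, and vital status.

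The terminal gap then closes, to within the visit window, for every patient reached. Treatment of patients not reached is left to the SAP. The cost is one extra telephone call per early stopper and a short edit in three places, with no new staff or procedures.

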7.2.4 Study Termination by Sponsor

This study may be terminated at any time by Albireo if significant safety concerns develop or, in the sponsor's judgment, there are no further benefits to be achieved from continuation of the study. In this event, Albireo/designee will inform the study investigators, institutions and all regulatory authorities.

Albireo may temporarily or permanently discontinue the study at an investigative site at any time for safety, ethical, compliance or other reasons. If this is necessary, Albireo will endeavor to provide advance notification to the site. If a site or the study is suspended or discontinued, the investigator/investigative staff will be responsible for promptly informing the Independent Ethics Committee (IEC)/Institutional Review Board (IRB) that this has happened. If required by local regulations, Albireo/designee will be responsible for informing the IEC/IRB and the Regulatory Authority of study or site discontinuation. In such an event, all study data and unused study drug must be returned to Albireo.

8 TREATMENT OF PATIENTS

8.1 Identity of Study Drug

A4250 will be supplied as capsules for oral administration. White opaque capsules filled with pellets containing A4250 will be provided. Two different capsule sizes will be available:

- Capsule size 0 that can be opened
- Capsule size 3 that should be swallowed intact. The size 3 capsules may be opened only under exceptional circumstances, e.g., patient cannot swallow the capsule intact.

Bottles with 34 capsules will be given to the patient at each visit. A patient who requires 2 or more capsules per day will be given multiple bottles. Refer to the Investigational Product Manual.

A 5-digit study drug number will identify study drug packs and will be detailed on the study drug label. Dispensing of study drug will be coordinated by the Interactive Web Response System (IWRS). The system will assign study drug number(s) using a packing list based on the patient's weight and dose level (either 120 µg/kg/day or 40 µg/kg/day) for dispensation at each dispensing visit. In case of technical issues accessing the system online, please see the IWRS site user manual for country-specific contact telephone numbers to the ICON HelpDesk 24/7 system support.

